***VOICE-CF: Vocal Biomarker Analysis for Health Condition
Detection in People with Cystic Fibrosis (CF)***

PROTOCOL

DATE 19 March 2021

CHIEF INVESTIGATOR

[name] (CI)

Professor of Respiratory Biology, University of Cambridge
Research Director and Honorary Consultant Physician, Cambridge Centre for Lung Infection
Royal Papworth Hospital NHS Foundation Trust
[name]
Tel: [name]
Email: [contact]

Investigation Sites: Royal Papworth Hospital, United Kingdom

Protocol Contributors: [name], Royal Papworth NHS Foundation Hospital
[name], BSC, University of Cambridge

Sonde Health
[name]
[name]

Protocol Identification Number: PO2706

Date of Protocol: 19 March 2021

Protocol Version Number: 3.0

Trial Sponsor: Royal Papworth Hospital NHS Foundation Trust
[name]
[name]
[name]

Contents

TRIAL OVERVIEW

- 1. **Trial Overview**
 - Primary Research Question
 - Study Design
 - Primary Outcome
 - Rationale

- 2. **Patient Recruitment**
 - Study Population
 - Inclusion Criteria.....
 - Exclusion Criteria
 - Recruitment Strategy.....

- 3. **Sample Size and Data Analysis**
 - Sample Size.....
 - Statistical Analysis.....

- 4. **Consent Process and Visit Schedule**
 - Visit.....
 - Daily Samples
 - Informed Consent Procedure

- 5. **Follow up Visits and Travel Expenses**

- 6. **Data Collection**
 - Data Collection Form Completion
 - Data Access / Sharing.....
 - Data Flow Chart
 - Storage of Documents.....
 - Retention of Documents.....
 - Monitoring and Auditing

- 7. **Adverse and Serious Adverse Events**
 - Recording & Reporting

- 8. **Amendments**
 - Amendment log

TRIAL OVERVIEW

1. Trial Overview

Primary Research Question

Study Design

This is a two-year single-centre, observational, prospective cohort study. We aim to recruit initially 100 and then, following interim analysis, up to 300 adult males and females with CF, who are already participating in the Project Breathe home monitoring service improvement project at Royal Papworth Hospital. The study is designed to run as a non-disruptive study with no impact on routine clinical practice. Participants will be enrolled for 12 months.

Primary Outcome

- 1) To determine whether vocal biomarkers can contribute to existing predictive algorithms for pulmonary exacerbations
- 2) To determine whether vocal biomarkers can substitute for other data collection methods, in particular spirometry and pulse oximetry.

Rationale

The aim of this study is to explore the potential of vocal biomarkers to assist in or improve the detection of health conditions in people with CF. The emphasis is on identifying onset and progression of pulmonary exacerbations.

Using their smartphone, participants submit daily voice samples that will be analysed for markers of various health conditions using labelled training data (physiological, activity and self-reported data) that is also collected on a daily basis. The Sonde voice sample collection and other home monitoring recordings will happen sequentially. Participants will continue with voice sample collection if admitted for a pulmonary exacerbation if they wish to.

Sonde Health is a health technology company with a platform that provides voice-enabled health detection and monitoring capabilities in brain, respiratory and muscular impairment. Analysis of vocal biomarkers can provide early insight into one's health and wellness. Sonde's API platform enables most companies and developers with Android or iOS mobile applications to integrate health condition detection and monitoring capabilities powered by voice.

Royal Papworth Hospital has demonstrated that daily recordings of a range of physiological parameters (e.g. spirometry, pulse oximetry, activity, heart rate, etc.) in combination with self-reported survey responses (e.g. general wellness, cough, sleep quality) in people with CF holds promise to more accurately track fluctuations in health condition, in particular the start of pulmonary exacerbations (PEX). These data are collected remotely at the study participant's home using remote/ virtual online tools, as part of a larger effort to take a more virtual approach to clinics. Smartphone-based collection of voice samples for vocal biomarker analysis is a natural extension of this approach.

We propose a phased approach that starts by enrolling 100 participants, who would provide daily voice recording on the Sonde app, in addition to continuing their ongoing daily data recordings described above.

Following interim analysis at 3 months from starting the study, we will then decide whether to expand to include up to 300 participants.

Schedule of Events

2. Patient Recruitment Criteria

Study Population

- Initially 100 and then a further 200 adult male and female CF patients
- 12 - month enrollment period

Inclusion

- Diagnosis of Cystic Fibrosis based on genetic testing and /or sweat chloride levels.
- Age between ≥ 18 to ≤ 65 years of age at time of consent
- Able to provide written informed consent
- Patients who are currently undertaking home monitoring / virtual clinics.
- Patients who have use of a smartphone

Exclusion

- Patients unable to provide written informed consent
- Patients who are currently not undertaking home monitoring / virtual clinics
- Lung transplant recipients.

Recruitment

- The planned recruitment target rate is:
 - Year 1: Initially *100 and then a further 200 patients after interim analysis.*
 - The recruitment rate has been calculated based on previous similar studies and recognized recruitment rates for this institution.

Section 3. Sample Size and Data analysis

Sample Size

Based on previous studies using vocal biomarkers to assess respiratory disorders (Stasak et al, 2020, submitted to IEEE ICHI on COVID-19 identification from voice; additional unpublished internal data gathered by Sonde Health on 3,000+ patients with asthma, COPD, and CHF), we expect to be able to correlate voice signals with other physiological signals with 20-30 participants. We would like to recruit between 100 and 300 participants to examine whether signal changes in the Sonde app provide useful additional information of impending acute pulmonary exacerbations.

Statistical Analysis

- All data collection i.e. voice, physiological and self-reported data will be jointly analyzed using a variety of statistical and machine learning techniques. The Sonde App data will be linked to other study data using the existing participant study ID, which participants will enter in the Sonde App. No identifiable information will be shared with Sonde.

4. Consent Process and Visit Schedule

Visit

- Patients will be approached for consent in one of the following ways (1) whilst attending their normal CF clinic outpatient appointment with hardcopy consent (2) a telephone call & discussion with documented verbal consent (3) email introduction with follow-up telephone call and email consent or (4) whilst an in-patient on the ward with hardcopy consent.

Daily Samples

- Each patient will collect daily short voice samples on the Sonde app using their personal smartphone device (iOS or Android) along with their other normal daily home monitoring data
- Each daily voice sample will take approximately one minute to complete.
- You will submit 2 identical voice samples daily during the study.
 - 1) There will be two identical voice sample recordings
 - a 6 second held vowel “ahhh” which will be done twice.

Informed Consent Procedure

- Patients will receive written and verbal information about the trial
- Patients interested in participating in the study will be provided with a study-specific patient information sheet and given time to consider the study. A member of the research team will contact the patient to discuss the study further and possible participation in the study.
- Written or verbal informed consent (which can be provided in the form of email or telephone) will be obtained by a member of the trial team after a suitable time has elapsed during which the patient has had ample time to read the information sheet, consider the trial and ask any questions. The Investigator must explain to each patient the nature of the study, its purpose, the procedures involved, the expected duration, the potential risks and benefits involved and any discomfort it may entail (*Ref. International Conference of Harmonisation of Good Clinical Practice (ICH/GCP) 5 4.8.7*)
- The ultimate responsibility for obtaining written or verbal or electronic informed consent lies with the Investigator, but this responsibility may be delegated to a suitably trained, and experienced person.
- Prior to the patient’s participation in the study, the written informed consent form must be signed and personally dated by the patient and by the clinician who conducted the informed consent discussion (*Ref. ICH/GCP 4.8.8*). Each box at the end of each statement on the consent form must be signed by the patient.
- Each subject must be informed that participation in the study is voluntary and that he/she may withdraw from the study at any time and that withdrawal of consent will not affect his/her subsequent medical treatment (*Ref. ICH/GCP 4.8.10*).
- A copy of the informed consent document will be given to the patient (*Ref. ICH/GCP 4.8.11*). One copy will be filed in the patient’s hospital case notes and a copy filed in the Trial Management File by the Clinical Research Nurses.
- The Clinical Research Nurse will ensure that the patient does not have any trial specific procedures prior to giving informed consent.
- If a patient withdraws their consent a line should be drawn diagonally through the consent form and labelled ‘consent withdrawn’ and signed and dated by a member of staff.

- The informed consent is also presented within the Sonde App before study participants can start their daily study activities (one-time after starting the study). Participants indicate agreement by checking an electronic box. The app also allows participants to review the consent information at any time via the app menus.

5. Follow-up Visits and Travel Expenses

Follow up Visits

There are no formal follow up visits. All patient data will be monitored by the research team to ensure data collection is occurring on a daily basis. If there are any problems with the data, patients will be contacted either via email or telephone to offer help and guidance to the patient if needed.

Patients will also have access to support from the research team via telephone / email if they are having problems with data collection.

Travel Expenses

There will be no compensation or inconvenience payments given for participating in the project.

6. Data Collection

Data Collection Form Completion

- The consent form and other project documents will be stored in the research office in a locked cabinet.
- All participant data will be linked-anonymized and stored on a secure password protected computer.
- All consenting participants will be registered on the study's registration log which will be filed in the study's site file. The registration log will include the participants name, date of birth and study ID.

Interim Analysis

An interim analysis will be conducted at the 1-year point after study start to further inform on how many patients will be needed to complete the study. We will file a protocol amendment with the ethics committee should this number differ significantly from that in the current protocol.

The current estimate of approximately 300 participants rests on assumptions detailed below. These assumptions will be refined at the interim analysis point with the data acquired up to that point, so that the powering can be assessed with greater confidence.

To determine the ability for the vocal biomarkers to assist in the prediction/ early detection of pulmonary exacerbations in people with cystic fibrosis, it is helpful to consider this performance in terms of sensitivity and specificity of the vocal biomarker data with respect to observed pulmonary exacerbations during the study. Other studies using these biomarkers in respiratory conditions have indicated that approx. 60% sensitivity and 60% specificity could be used as an approximate and somewhat conservative performance level. Sensitivity and specificity calculated from the collected data will be used to calculate odds ratio (2.25 at the given sensitivity and specificity) with a 95% confidence interval and p-value according to customary statistical methods. At the stated assumption around performance, about 60 pulmonary exacerbations would need to be observed and examined to have a p-value at 0.05.

[figure not shown]
From clinical experience in the CF clinic, it can be estimated that following roughly 100 patients with CF over a 12-month period will result in approximately 60 pulmonary exacerbations. Vocal biomarker models are gender dependent, so to assess this level of significance in both genders would require a total of 200 patient participants. Accounting for an as yet unknown degree of missing data and drop-outs from the study would further increase the sample size estimate to somewhere between 200-300.

At the 12-month interim analysis points all figures used in these calculations can be refined from the observations made up to that point.

Data Access / Sharing

- The Sonde health app will collect linked anonymized data. All data will be linked-anonymized and uploaded to Sonde's cloud-based server systems, which meet HIPAA and GDPR requirements. Sonde uses Amazon Web Services (AWS) for all data collection and app deployment. Documentation is available upon request. Collected data is transferred through secure (HTTPS) Protocol and is stored in encrypted form in AWS.
- The home monitoring equipment linked-anonymized data is already being uploaded to a secure NHS approved web-based site to allow researchers within the University of Cambridge to analyse it via Microsoft Azure which implements the transmission integrity and confidentiality control by ensuring that cryptography is implemented through a hybrid model. The following is a high-level list of the symmetric and asymmetric keys used for encrypting and protecting confidentiality of data.
 - Use AES for symmetric encryption/decryption
 - Use 128-bit or better symmetric keys
 - Use RSA for asymmetric encryption/decryption and signatures
 - Use 2048-bit or better RSA keys
 - Use SHA-256 or better (SHA-384, SHA-512) for hashing and message- authentication codes.
- Sharing of data between Royal Papworth Hospital and Sonde is as noted below:
 - Sonde will share with Royal Papworth, vocal biomarkers including voice feature level information that enables health detection research, with some limitations to protect Sonde IP and metadata collected on the Sonde app.
 - Royal Papworth will share with Sonde daily home monitoring data, participant demographics and basic medical history / comorbidities.
 - Data sharing between Sonde and Royal Papworth is planned during each 3-month increment and upon study completion.

Data Flow Chart

Storage of Documents

- There will be minimal storage of documents. The only documents that will be stored in paper form will be the consent forms and any letters of approvals or other paper related documents which will be kept in a locked filing cabinet in a locked room.

Retention of Documents

- All study documentation will be stored for 15 years after the last patient has completed their last study visit.
- Documentation will be archived in a fire safe, secure Sponsor approved archive facility.

Monitoring and Audit

- All study-related records will be made available upon request of the monitor, auditor, Sponsor, R&D, REC, MHRA or other regulatory authority.
- The project data will be monitored by the Research Officer quarterly. The first five patients along with the site and sponsor files will be monitored. Monitoring will be increased if any issues are found.

Section 7. Adverse and Serious Adverse Events

The definition of an adverse event is: 'Any untoward medical occurrence in a patient which does not necessarily have a causal relationship with this treatment'. This includes 'any unfavourable and unintended sign (including an abnormal laboratory finding), symptom or disease temporally associated with the study drug'. This may include, for example, a cold or an accident.

The definition of a serious adverse event is one that fulfils at least one of the following criteria:

- Is fatal- results in death
- Is life threatening

- Requires inpatient hospitalization or prolongation of existing hospitalization
- Results in persistent or significant disability/incapacity

OR

- Is a congenital anomaly/birth defect

The definition of a suspected unexpected serious adverse reaction (SUSAR) is a serious adverse event that is thought to be possibly or definitely related to the study drug.

Recording and Reporting

- As there is no therapeutic intervention involved in this study, we do not anticipate any risks
- We do not expect to have any AEs or SAEs
- All research staff in contact with patients are responsible for noting adverse events that are reported by the patient and making them known to the Principal Investigator.
- At each visit or study assessment, adverse events that have occurred since the previous visit should be elicited from the patient. The event should be detailed in the patient's notes, as source document verification, including the start date (if known) and the end date.
- The action taken regarding the study procedure should be documented
- Document any treatment/medication given for the event, including the dates the treatment/medication was commenced and the date it was stopped/changed, if applicable (an example of an AE form is in section 10 of the site file section). Documenting of adverse events is the responsibility of the Principal Investigator, Co-Investigator and Clinical Research Nurse/Assistant
- Events, which are ongoing at the final study visit, should be followed up as clinically indicated.
- All serious adverse events (SAEs) and suspected unexpected serious adverse reactions (SUSARS) will be documented as above using the appropriate reporting documentation in section 10 of the site file documents.
- SUSARS must be reported to the Sponsor within 48 hours of the Chief / Principle Investigator/Clinical Research Nurse being aware.
- All Unexpected SAEs and SUSARs should be reported to the hospital R&D department and may be require analysis through the hospital incident reporting system.
- SUSAR reports to be submitted to the main REC (*timelines to be specified*)
- Expected SAEs need to be reported to the Main REC in the annual REC report; the REC who performed the locality assessment does not need to be informed.
- Store all completed SAE forms with the patient's study documentation.

8. Amendments

Substantial amendments will be submitted to the Research Ethics Committee for review and approval.

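### Section 3 allows 100 participants for the exacerbation question, but Section 6 requires 200 before losses for significance in each gender; at 100 that analysis has half the events required

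*Protocol*

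**What the plan says.** The Sample Size text in Section 3 gives one range for the question of impending exacerbations: "We would like to recruit between 100 and 300 participants to examine whether signal changes in the Sonde app provide useful additional information". It also expects 20-30 participants to be enough to correlate voice with physiological signals.

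The Rationale in Section 1 starts with 100 people and makes growth conditional on an interim analysis: "we will then decide whether to expand to include up to 300 participants".

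The derivation is in Section 6, under Interim Analysis:
- Performance: "approx. 60% sensitivity and 60% specificity could be used as an approximate and somewhat conservative performance level".
- Events: "about 60 pulmonary exacerbations would need to be observed and examined to have a p-value at 0.05".
- Event rate: "following roughly 100 patients with CF over a 12-month period will result in approximately 60 pulmonary exacerbations".
- Because voice models differ by gender: "so to assess this level of significance in both genders would require a total of 200 patient participants".
- Missing data and drop-out "further increase the sample size estimate to somewhere between 200-300".

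The same text puts the current estimate at approximately 300 and promises an amendment to the ethics committee if the number needed differs significantly from the protocol's.

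**The concern.** Two sections size the same question with different lower limits: 100 in Section 3, and 200 before any loss in Section 6. The ranges overlap, but overlap does not reconcile the limits. Nothing in the protocol explains why 100 would be enough for inference within each gender, which is the basis on which Section 6 arrives at 200.

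Stopping at 100 is a permitted outcome. Such a study would lie within the size given in Section 3 while having about half the events that Section 6 requires for each gender. A non-significant result in men or in women could then be reported as evidence against voice biomarkers, when the plan's own figures show that it was the likelier result even if the assumed performance is true.

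**Working it through.** **Inputs (Section 6).** Sensitivity 0.60; specificity 0.60; about 60 exacerbations for p = 0.05; about 60 exacerbations per 100 patients over 12 months, i.e. 0.6 per patient-year; the requirement applies in each of two genders. Not given: number of control observations, drop-out rate, power target, sidedness. I take the test as two-sided, to match the 95% interval.

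**1. Reproduce the plan's figures.**
- Odds ratio = (0.6/0.4) × (0.6/0.4) = 2.25, as stated.
- With n events and n controls (equal numbers are my assumption), the smallest n giving p ≤ 0.05 at exactly 60%/60% is 49 by Wald or uncorrected chi-square and 58 with continuity correction. So about 60 reproduces.
- At 60 + 60: SE of log OR = √(1/36 + 1/24 + 1/24 + 1/36) = 0.373; z = 0.811/0.373 = 2.18; Wald p = 0.030, Fisher p = 0.044; 95% CI 1.08-4.67.
- Patients: 2 genders × 60 = 120 events; 120/0.6 = 200, as stated.
- With assumed losses of 10%, 20%, 30% and one third, 200/(1 − loss) = 223, 250, 286 and 300, consistent with the stated 200-300.

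**2. Events if the study stops at 100.**
- 100 × 0.6 = 60 in total, or about 30 per gender with an even split and no loss. Against 60 per gender this is 30/60 = 50%.
- Pooled over genders, the 60 events equal the plan's figure. Assumed losses of 10%, 20% and 30% would leave 54, 48 and 42.

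**3. What 30 events per gender give at 60%/60%, one control per event.**
- SE = √(1/18 + 1/12 + 1/12 + 1/18) = 0.527; z = 0.811/0.527 = 1.54.
- p = 0.12 (Wald) or 0.20 (Fisher); 95% CI 0.80-6.32.
- Power is about Φ(1.54 − 1.96) = 0.34. With 60 + 60 it is about 0.58-0.59.

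**4. Sensitivity to the number of controls, 30 events.** SE = √(1/18 + 1/12 + 1/(0.6c) + 1/(0.4c)) for c controls.

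| Controls | Wald p | Fisher p |
|---|---|---|
| 30 | 0.124 | 0.196 |
| 150 | 0.047 | not computed |
| 300 | 0.038 | 0.051 |
| 3000 | 0.030 | 0.038 |

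With many controls, however, the plan's figure of about 60 no longer reproduces: 60 events with 600 controls give Wald p = 0.003.

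**5. A check that needs no control ratio.** If 60 events give p = 0.05 (z = 1.96) at whatever ratio the plan used, halving events and controls together gives z = 1.96/√2 = 1.39 and p of about 0.17. This lies inside the 0.12-0.20 range of step 3.

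**The case against.** The strongest reply is that 100 is a first stage and not a size claimed to be sufficient. Sections 1 and 2 describe an initial 100 followed by up to 200 more, Section 6 estimates about 300, and its amendment clause may well apply to a final size of 100. Section 3 says only that the investigators would like to recruit this range in order to examine the question. This stands in part: the protocol nowhere asserts that 100 gives significance. But Section 3 does state 100 as the lower end for this question without calling it a stage, and the amendment clause needs one agreed number to compare against.

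The second reply is that 100 participants do deliver the plan's 60 events. This stands for a pooled analysis before losses. Voice models that differ by gender do not rule out pooling their classifications for evaluation. A reader might infer that a study of 100 falls short for every exacerbation analysis. The document does not support that, because the 200 arises only from the wish for significance in both genders.

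A reader might also infer that significance within a gender is out of reach at 100. That too goes beyond the document. Power of about 34% is roughly one chance in three, and Section 6 calls 60%/60% somewhat conservative. If 20 of 30 were classified correctly in each group, 30 + 30 would give Wald p = 0.011 and Fisher p = 0.019.

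Finally, the p-values and power rest on a control count that the protocol text does not give. A figure not reproduced in the available copy follows the event calculation and may contain it. Equal numbers are a fair reconstruction, but the values should be read with the range in step 4. The comparison of 100 with 200 needs no such assumption.

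**Conclusion.** The point holds as an internal inconsistency. Each section's arithmetic is sound: 2.25, about 60 and 200 all reproduce. The lower limit of 100 in Section 3 is not supported by Section 6 for inference within each gender. At 0.6 events per patient-year, an even split and no loss, stopping at 100 gives about 30 events per gender against 60 required. Loss lowers the count further, and an uneven split worsens the position of the smaller group.

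At 60%/60% with one control per event, significance within a gender is not expected (p about 0.12-0.20, power about 34%) but is possible. With 150 controls p is about 0.05, and with 3000 about 0.03. The phased design and the amendment clause soften the problem without removing it. It should be corrected, and the correction is small.

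**What to change.** - In Section 3, give 200-300 as the size for gender-specific exacerbation inference, in line with Section 6.
- Describe the first 100, there and in Sections 1 and 2, as a first phase. It supports the voice-physiology correlation (for which the plan expects 20-30 to suffice) and a pooled, gender-stratified exacerbation estimate with its confidence interval.
- State that if the study stops at 100, gender-specific results are descriptive and a non-significant result is not read as evidence against voice biomarkers.
- Note that the amendment clause in Section 6 may apply if the final number differs significantly from the approximately 300 estimated.

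The cost is wording in Sections 1 to 3. What is claimed for the first phase becomes less favourable; no extra patients or procedures are needed.

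### Primary outcome 1 asks what voice adds to existing exacerbation algorithms, but the only test the protocol specifies and sizes is the odds ratio of voice alone

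*Protocol*

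**What the plan says.** **The question.** Protocol Section 1, Primary Outcome, item 1: "To determine whether vocal biomarkers can contribute to existing predictive algorithms for pulmonary exacerbations". Section 3, Sample Size, gives the purpose of recruiting 100 to 300 people: "to examine whether signal changes in the Sonde app provide useful additional information of impending acute pulmonary exacerbations". Both ask what voice contributes beyond what is already available. The Rationale describes what that is: daily spirometry, oximetry, activity, heart rate and self-reported symptoms.

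**The calculation.** Section 6, Interim Analysis, treats the task differently: "it is helpful to consider this performance in terms of sensitivity and specificity of the vocal biomarker data with respect to observed pulmonary exacerbations". Its planning assumption is that "approx. 60% sensitivity and 60% specificity could be used as an approximate and somewhat conservative performance level". Sensitivity and specificity from the collected data are to be converted into an odds ratio (2.25 under that assumption), "with a 95% confidence interval and p-value according to customary statistical methods". On this basis "about 60 pulmonary exacerbations would need to be observed and examined to have a p-value at 0.05". That count is matched to roughly 100 patients followed for 12 months, doubled to 200 so that each sex can be assessed, and raised to 200-300 for missing data and drop-out.

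**The analysis text.** Section 3, Statistical Analysis, says that voice, physiological and self-reported data will be analysed together by several statistical and machine-learning methods, linked by study ID. It names no model with and without voice, no comparator and no measure of improvement.

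**The concern.** The Section 6 odds ratio comes from a two-by-two table of voice against exacerbation. The existing algorithm does not appear in it. If the voice signal is a noisy reflection of what spirometry, oximetry or symptoms already show, voice will be associated with exacerbations, and the odds ratio will exceed 1, although voice improves no prediction.

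Two things are at stake. First, a significant odds ratio could be taken as a positive answer to outcome 1 when it answers a different question. Second, Section 6 says that the figures in this calculation will be refined at the 12-month interim analysis and used to judge how many patients are needed. Refining stand-alone sensitivity and specificity would re-size the study on a quantity that is not the one in outcome 1.

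**Working it through.** **1. Reproduce the protocol's figures.** Inputs from Section 6: sensitivity 0.6, specificity 0.6, 60 exacerbations, significance level 0.05. Assumed because not stated: 60 comparison windows (1:1) and a two-sided test.

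- OR = [Se/(1−Se)] × [Sp/(1−Sp)] = 1.5 × 1.5 = 2.25, as stated.
- Expected table: 36 positive and 24 negative among exacerbation windows; 24 positive and 36 negative among comparison windows.
- SE(log OR) = √(1/36 + 1/24 + 1/24 + 1/36) = 0.373; ln 2.25 = 0.811; z = 2.18; Wald p = 0.030; 95% CI 1.08 to 4.67.
- Pearson p = 0.028; Yates p = 0.045; Fisher p = 0.044.
- Smallest group size reaching p ≤ 0.05: 49 (Wald) or 58 (Yates). Fisher crosses between 55 (p = 0.056) and 60 (p = 0.044).

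So about 60 is reproduced under Yates or Fisher with 1:1 windows. The arithmetic is sound; the issue is which question it addresses.

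**2. Can this test be significant when voice adds nothing?** The documents give no performance for the existing algorithm, so a range is assumed: an existing alarm with sensitivity = specificity = s, at 0.7, 0.8 or 0.9. Voice agrees with the alarm with probability q and is otherwise unrelated to exacerbation, so its added information is exactly zero. Choose q so that voice alone has 60%/60%:

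s·q + (1−s)(1−q) = 0.6, hence q = (s − 0.4)/(2s − 1).

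Simulation with 20,000 runs per row, 60 + 60 independent windows. The adjusted test is Mantel-Haenszel, stratified by the existing alarm.

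| s (assumed) | q | Stand-alone OR significant | Voice given existing alarm significant |
|---|---|---|---|
| 0.7 | 0.750 | 61.4% | 5.1% |
| 0.8 | 0.667 | 61.1% | 4.9% |
| 0.9 | 0.625 | 61.0% | 4.8% |

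**3. Second construction, continuous scores.** Voice at 60%/60% has a standardised separation of 2 × z(0.6) = 0.507. If voice correlates 0.5 with the existing score and carries nothing else, the score's separation is 0.507/0.5 = 1.013 and its AUC is Φ(1.013/√2) = 0.763. Two sets of 4,000 runs at each size gave:

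- Stand-alone test significant: about 61% (60 + 60) and 86-88% (120 + 120).
- Voice given the score significant: 5.1% (60 + 60) and 5.2-5.5% (120 + 120).

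More data make the stand-alone result more often significant, while the adjusted test stays near its 5% null rate.

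**4. The converse.** With 60 + 60 windows and voice truly at 60%/60%, power of the stand-alone test is about 59% (normal approximation), so about 41% of studies would be non-significant. A marker with a modest association of its own can still carry information that the algorithm lacks. A non-significant odds ratio therefore does not show that voice adds nothing.

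**5. What cannot be computed.** A sample size for the increment needs the existing algorithm's performance and its correlation with voice. The protocol gives neither.

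**The case against.** The strongest reply is that the odds ratio is not put forward as the test of outcome 1. It stands under Interim Analysis, as the assumptions behind the estimate of about 300 participants, and is introduced in tentative language. Section 3 promises a joint analysis, which is where added value would naturally be assessed. The comparison may be set out in a statistical analysis plan that is not shown, and a protocol may leave such detail there. The study is observational and exploratory.

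Much of this stands, and it rules out several stronger readings. A reader might infer that the odds ratio is the declared primary test, or that a comparison with and without voice will never be made; the protocol says neither. A reader might take 60%/60% as a success target; it is a planning assumption. A reader might expect a significant result to lead to a recommendation for daily voice recording; no passage says so. The low positive predictive value implied by 60%/60% and rare exacerbations is a separate matter that depends on window lengths the protocol does not give.

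The illustration is also built so that voice adds exactly nothing. It shows that the stand-alone test cannot separate that case from a useful one, not that the case is likely.

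What the reply does not remove: Section 6 commits to computing this odds ratio and its p-value from the study data, and the 60, 200 and 200-300 figures all rest on it. An unseen plan could add the right comparison, but it would not make those figures apply to outcome 1.

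**Conclusion.** The point holds as a mismatch between the question and the only test that the protocol specifies and sizes. Outcome 1 and the stated purpose of recruitment concern added information; the sized quantity is voice alone. With an existing alarm assumed at 70% to 90% sensitivity and specificity, and voice at 60%/60% merely echoing it, the stand-alone odds ratio is significant in about 61% of studies of 60 + 60 windows, against about 5% for a test of voice given the alarm. These percentages assume 1:1 independent windows and a two-sided 5% level; repeated days within a participant would change them. The direction does not depend on the assumed performance of the existing algorithm: both constructions give it. The documents do not support saying that voice adds nothing, or that the increment will go unexamined.

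**What to change.** In the protocol:

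- State that outcome 1 is assessed by comparing the existing algorithm with the existing algorithm plus voice, in the same participants and windows. Name which existing algorithm is the comparator. Suitable measures are, for example, a test of voice adjusted for the existing score and the change in discrimination, with a confidence interval that allows for repeated days within participant. The technical detail can go in the statistical analysis plan.
- Keep the stand-alone odds ratio as a secondary, descriptive result.
- State that the 60-exacerbation and 200-300 figures apply to the stand-alone odds ratio only.
- Use the 12-month interim analysis in Section 6 to estimate the increment and its precision, and judge the number of participants from that. Section 6 already foresees a protocol amendment if the number changes significantly.

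**Cost.** No new data are needed: voice and home-monitoring data are collected daily and linked by study ID. The change goes beyond analysis wording, because the sample-size rationale must be restated and cannot be completed until interim data or an outside estimate of the increment is available. The increment will probably be smaller and less precisely estimated than the stand-alone effect, so the result may look less favourable and the required number may rise.
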